3.2.1.2 Secondary efficacy analysis

All secondary and exploratory analyses will be performed on PP population only.

Selection of the optimal dose range for peptide mass and radioactivity of ^{68}Ga -OPS202 will be based on the provided descriptive statistics for all secondary and exploratory efficacy endpoints, in addition to primary endpoint.

Key Secondary Endpoint:

a) Image quality

Quantitative measure:

For each PET assessment, image quality will be quantitatively measured by the tumour-to-background ratio, which will be obtained using the mean of all lesions tumour-to-backgrounds, for each of the four following organs:

- Liver
- Lymph nodes
- Bone
- Lungs

For up to five most avid lesions per organ that are confirmed by SOT, the tumour-to-background ratio will be computed as lesion SUV_{mean} divided by the SUV_{mean} of the subject's reference tissue (tumour-free liver or aortic blood).

Tumour-to-background ratio is a unit-less measure. A high tumour-to-background ratio indicates high effectiveness of ^{68}Ga -OPS202 as a diagnostic agent.

Tumour-to-background ratio will be analysed using descriptive statistics, presented for each of the four organs and for:

- each of the six combinations of injected peptide/radioactivity dose range
- each of the two peptide mass dose ranges
- each of the three radioactivity dose ranges

Individual values of tumour-to-background ratio will be listed by subject, by organ and by visit. Background location will be specified (L: Liver, B = Aortic blood).

Qualitative measure:

A qualitative analysis of the image assessed by the independent blinded readers will be performed to back up the quantitative quality measured by tumour-to-background analysis. This qualitative assessment will be performed using a quality score.

For each PET/CT and PET assessment, each independent blinded reader will perform a direct comparison of the two ^{68}Ga -OPS202 scans (Visit 2 and Visit 3, that have with different peptide and radioactivity doses). He/she will note which of the pair provides superior images based on overall image quality and lesion count, attributing a score for each assessment.

The score for the assessment having superior images will be set to “1”, and score for the assessment not selected will be set to “0”. In case of equal quality, both assessments will have a score of “1”.

Values will be available in the database provided by ICL.

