Quality score will be analysed using descriptive statistics (frequencies and percentage), presented for:

- each of the six combinations of injected peptide/radioactivity dose range
- each of the two peptide mass dose ranges
- each of the three radioactivity dose ranges

Two sets of analysis will be performed for quality score:

- Based on assessment by reader A
- Based on assessment by reader B

Besides, readers scores will also be summed up together and presented for each of the six combinations of injected peptide/radioactivity dose range.

Individual values of quality score as well as which scan do reader prefer and reason for selecting scan 2 or 3 will be listed per reader, then by subject and by visit for both types of assessment (PET/CT and PET).

Other Secondary Endpoints:

b) Lesion SUV_{max}

For each PET assessment, lesion SUV_{max} (unit-less measure) will be measured for each lesion, up to a maximum of five most avid lesions per organ that are confirmed by SOT. In order to obtain a unique measure per organ, mean of the SUV_{max} will be computed within each of the four following organs:

- Liver
- Lymph nodes
- Bone
- Lungs.

Values will be available in the database provided by ICL.

Lesion SUV_{max} will be analysed using descriptive statistics, presented per organ and for:

- each of the six combinations of injected peptide/radioactivity dose range
- each of the two peptide mass dose ranges
- each of the three radioactivity dose ranges.

Individual values will be listed by subject, by organ and by visit.

- c) Absolute number of lesions detected by ^{68}Ga -OPS202, both as standalone and also compared to SOT

For each PET/CT and PET assessment, the number of lesions detected by ^{68}Ga -OPS202 and by SOT will be reported for each of the five following anatomic sites:

- Primary site of GEP-NET
- Lymph nodes
- Liver
- Axial/appendicular skeleton (Bones)
- Lungs

Values will be available in the database provided by ICL.

Absolute number of lesions detected by ^{68}Ga -OPS202 and difference with number of lesions detected by SOT will be analysed using descriptive statistics (for continuous variable), presented per anatomic site and for:

- each of the six combinations of injected peptide/radioactivity dose range
- each of the two peptide mass dose ranges
- each of the three radioactivity dose ranges

Also, for comparing lesions detection between ^{68}Ga -OPS202 and SOT, the following analyses will be performed:

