For lesion-based approach (per organ), following organs will be analysed: Primary site of GEP-NET, Lymph nodes, Liver, Axial/appendicular skeleton, Lungs. In case no lesions were detected by the SOT, sensitivity cannot be computed due to null denominator. Therefore only organs with lesions detected by SoT will be analysed for sensitivity.

To allow for computation of sensitivity, detected lesions will be counted from the “Lesion Matching Table” provided by ICL.

Additionally, an organ-based specificity analysis will be performed, based on PET/CT assessments.

For each organ:

- If there are 0 lesions detected in an organ on both ^{68}Ga -OPS202 scan and SOT, it will be counted as TN.
- If there is at least 1 lesion detected in an organ on ^{68}Ga -OPS202 scan but not on SOT, it will be counted as FP.

Example for a given subject, a given visit VX:

	At least one lesion detected by ^{68}Ga -OPS202 at Visit VX	At least one lesion detected by SOT	Type of lesion for analysis
Primary site of GEP-NET	No	Yes	FN
Lymph nodes	Yes	No	FP
Liver	Yes	Yes	TP
Bones	No	No	TN
Lungs	Yes	Yes	TP

Specificity will be calculated using the following formula:

$$\text{Specificity} = \frac{TN}{TN + FP}$$

In the example above, ^{68}Ga -OPS202 PET/CT assessment will have a specificity equal to 0.5 when compared to SOT.

Subject-based and lesion-based sensitivity along with organ-based specificity will be summarised using descriptive statistics for:

- each of the six combinations of injected peptide/radioactivity dose range
- each of the two peptide mass dose ranges
- each of the three radioactivity dose ranges

It will be also summarised using descriptive statistics for following five radioactivity dose groups:

- ^{68}Ga -OPS202 PET/CT at 40 to 80 MBq
- ^{68}Ga -OPS202 PET/CT at 100 to 140 MBq
- ^{68}Ga -OPS202 PET/CT at 160 to 200 MBq
- ^{68}Ga -OPS202 PET/CT at 100 to 200 MBq *
- ^{68}Ga -OPS202 PET/CT at 40 to 200 MBq *

Note: *A subjects' scan will use either his visit 2 or visit 3 scan, and not both. ^{68}Ga -OPS202 PET/CT at (100-200 MBq) and (40-200 MBq) will use the same subjects except the scan/visit with the lowest dose will be read. i.e.

- For 100-200 MBq, will choose Arm: A visit3, B visit2, C visit 2
- For 40-200 MBq, will choose Arm: A visit2, B visit2, C visit 3

Individual values of subject-based, lesion-based sensitivity and organ-based specificity will be listed by subject and by visit for this assessment (PET/CT).

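### The uptake endpoints set no common lesion set for a subject's two scans, so in organs with few lesions a scan that misses faint ones can score higher

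*SAP*

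**What the plan says.** SAP 3.2.1.2 a) sets the unit of the key secondary endpoint: "For each PET assessment, image quality will be quantitatively measured by the tumour-to-background ratio". The per-organ value is one "which will be obtained using the mean of all lesions tumour-to-backgrounds". The lesions are restricted as follows: "For up to five most avid lesions per organ that are confirmed by SOT", and "the tumour-to-background ratio will be computed as lesion SUV_{mean} divided by" the SUVmean of the reference tissue.

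Part b) measures SUVmax on each PET scan for "up to a maximum of five most avid lesions per organ that are confirmed by SOT" and averages it within the organ. Part g) applies the same unit and selection to the SUVmax ratio, without saying how lesions are combined.

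On interpretation, part a) states: "A high tumour-to-background ratio indicates high effectiveness of" the product as a diagnostic agent. The opening of 3.2.1.2 says that the dose range will be selected "based on the provided descriptive statistics for all secondary and exploratory efficacy endpoints, in addition to primary endpoint".

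Four things bear on which lesions enter:
- Neither document says that the lesions must be the same at Visit 2 and Visit 3.
- No value is assigned to a standard-of-truth lesion that one scan misses, and SAP 3.2.3.1 excludes imputation for efficacy data.
- The imaging core lab supplies a Lesion Matching Table, but the SAP names it only under e): "To allow for computation of sensitivity, detected lesions will be counted from the" that table.
- Protocol 7.3 leaves the calculation of the tumour-to-background ratio and SUVmax to the imaging review charter.

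**The concern.** If each scan contributes its own brightest confirmed lesions, the two averages for a subject can be taken over different lesions. This can happen in two ways.

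First, when an organ has few confirmed lesions, a scan that fails to show the faint ones averages over the bright ones only. Its score rises because it saw less.

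Second, when an organ has more than five, choosing the top five on noisy values also picks upward noise, and picks more of it on the noisier scan.

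The SAP reads a higher ratio as better and lets these endpoints inform the dose range. The protocol synopsis anticipates a poor diagnostic signal at 40-80 MBq, particularly at high body mass index, so scans of unequal quality within a subject are foreseeable. With no tests or confidence intervals, the reader will have little beyond cell means to judge by. A tumour-to-background ratio that favours one combination while the lesion count favours another could then be taken for a real trade-off when it comes from which lesions were averaged.

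**Working it through.** **The plan's own figures.** 24 subjects × 2 scans = 48 scans; 48 / 6 = 8 per combination, 48 / 2 = 24 per peptide range, 48 / 3 = 16 per activity range. These agree with the SAP. The documents give no figure for a selection effect and no lesion-level spread, noise or miss rate, so the sizes below rest on stated assumptions.

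**Can organs have few lesions?** Protocol 4.1 asks for at least two lesions in at least one key organ. Protocol 4.2 uses five lesions in total and 25 per organ as its limits. Both are counted on the earlier somatostatin receptor scan. The ratio is reported separately for four organs, so organs with fewer than five lesions and organs with many are both allowed.

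**Worked example.** Three lesions with ratios 12, 6 and 3 average 21 / 3 = 7.0. If the scan misses the lesion at 3, the average is 18 / 2 = 9.0, which is 2 / 7 = 29% higher for the scan that saw less. With ten lesions (20, 15, 12, 10, 8, 6, 5, 4, 3, 2.5), the top five average 65 / 5 = 13.0. Missing the last two leaves 13.0, a change of 0%.

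**Simulation.** 100,000 organ pairs per setting, with identical true uptake on both scans. Assumptions, none from the documents:
- K lesions per organ, with log-normal true ratio, median 6 and log-SD 0.6.
- The better scan shows every lesion. The poorer scan misses those with true ratio below 4, a share of Φ((ln 4 − ln 6) / 0.6) = Φ(−0.68), about 25%.
- Score = mean of the top five detected lesions, ranked on each scan's own values.
- For the noise runs, all lesions are detected, with lesion-level noise of 10% on the better scan and 20% or 30% on the poorer.

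Excess score of the poorer scan:

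| Lesions K | Missed faint lesions only | Noise only, 20% v 10% | Noise only, 30% v 10% |
|---|---|---|---|
| 2 | +15.3% | +0.1% | 0.0% |
| 3 | +18.6% | 0.0% | +0.1% |
| 5 | +19.7% | 0.0% | 0.0% |
| 7 | +3.9% | +0.5% | +1.3% |
| 10 | +0.2% | +1.0% | +2.7% |
| 15 | 0.0% | +1.6% | +4.1% |
| 25 | 0.0% | +2.3% | +5.9% |

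With both mechanisms (25% missed, 20% v 10% noise), the poorer scan scores higher in 73% of organ pairs at K = 3, 81% at K = 5 and 53% at K = 10. On matched lesions the shares are 48%, 48% and 53%.

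**Can it hide a real loss?** Take the combined excess of 18.7% (K = 3), 19.8% (K = 5) and 1.2% (K = 10), and let the poorer scan truly lose 10% of contrast: 1.187 × 0.9 = 1.068, 1.198 × 0.9 = 1.078 and 1.012 × 0.9 = 0.911. The poorer scan still leads by about 7% to 8% at 3 or 5 lesions, and trails by about 9% at 10.

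**Does matching cure it?** Restricting to lesions detected on both scans brings the missed-lesion excess to 0.0% at every K. It does not remove the noise part if the five are ranked on the average of the two scans: at 20% v 10% it is +1.1% at K = 10 (against +1.0% unmatched) and +2.3% at K = 25 (unchanged). That part goes only if the choice ignores the PET values. In this model detection depends on true contrast; if it also depends on noise, matching alone may leave a remainder.

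**The case against.** The strongest reply is that the SAP does not say the lesions are chosen separately, and that the charter, to which Protocol 7.3 assigns the calculation, may fix one set. This stands as a limit. A reader might infer that separate selection is certain; it is only the natural reading of a measure defined scan by scan. But the SAP defines the endpoint, and one sentence there would settle it.

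Second, the candidates must be confirmed by a standard-of-truth built from both CTs together, so both scans draw on one pool. True, and this removes false positives. It does not make both scans use the same members of the pool.

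Third, other measures work against the poorer scan: the relative lesion count, absolute counts, sensitivity, the paired reader score and the liver signal-to-noise ratio. SAP 3.2.1.1 bases dose selection on the highest relative lesion counts, with the secondary endpoints in addition. A reader might infer that the trial will therefore choose the worse dose; the documents do not support that.

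Fourth, the tumour-to-background ratio uses SUVmean, and a listing of measurements per lesion is planned. The listing would help to expose unequal lesion numbers, but it does not change the summary.

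Finally, a reader might take an extreme illustration as the expected size. Four lesions at 10, 6, 4 and 2 with half missed go from 5.5 to 8.0, or +45%. Nothing in the documents suggests losses of that order. The protocol speaks of a poor signal, or one near or below optimal for some subjects, and states neither a miss rate nor a noise level.

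**Conclusion.** The concern holds in a conditional form. As written, the three uptake measures have no common lesion set and no value for a missed lesion, so they can score the scan that sees less more highly. The effect is confined to organs with roughly seven confirmed lesions or fewer: about +15% to +20% at 2 to 5 lesions, about +4% at 7 and near zero from 10, given equal true uptake and about 25% of lesions missed. Selection on noise is a smaller matter in other organs: about 1% to 2% at 10 to 25 lesions for 20% against 10% noise, and nothing at five or fewer. The two should not be added together as if they acted in full on the same organ. The direction and the conditions are robust; the percentages depend on the assumptions.

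The overall dose choice need not be wrong, because the primary endpoint moves the other way when lesions are missed. What is lost is the ability to read a disagreement between the key secondary and the primary endpoint, and so to use the former to refine the dose range. The change should be made, and it is inexpensive.

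**What to change.** In SAP 3.2.1.2 a), b) and g), and in the charter, state that:
- The main comparison uses one lesion set per subject and organ, restricted to standard-of-truth lesions matched on both scans through the standard-of-truth list and the Lesion Matching Table.
- Where more than five lesions qualify, they are chosen by a rule that does not use the PET values, for example from the CT standard-of-truth list.
- Within-lesion paired differences are summarised, and the number of contributing lesions is shown for each cell.
- The scan-wise top-five result is kept as supportive.

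The cost is wording in two documents and some reprogramming; the matching table is already to be delivered, and no further scans or subjects are needed. There are two downsides. Lesions seen on only one scan leave the uptake comparison, although they still count in the lesion-count endpoints. The chosen set may also no longer be the most avid lesions, which departs from the protocol's description of these endpoints and should be recorded in SAP section 5.

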**Test product, dose, mode of administration:**

Ga-OPS202 is a diagnostic medicinal product with 3 main components, namely:

- Ga, a positron emitter radionuclide with a half-life of 68 min
- NODAGA, a chemical chelator group, and
- JR11, an antagonist somatostatin analogue that binds to sst2 receptors

OPS202 (cold kit) is available for clinical trials in a 50 µg peptide mass dose vial and is radiolabeled using a Ge/Ga-generator. The radiolabelled OPS202 (Ga-OPS202) consists of 50 µg of peptide in a total volume of 6 mL (8.33 µg/mL). Sampling of 0.5 mL for quality control yields 5.5 mL solution from which the volume to be injected into the subject is withdrawn. This volume is calculated to obtain the target peptide mass dose and the desired radioactivity dose.

The calculation of the volume takes into account the different components that determine the final radioactivity dose. The subject will be exposed to, in particular:

- The amount of Ga eluted from the generator, which depends on the latter's half-life
- The time elapsed between OPS202 (cold kit) radiolabelling and the injection of Ga-OPS202 to the subject (decay of Ga), the variation of which is a tool to adjust the final peptide/radioactivity dose to be injected
- The required peptide mass dose and radioactivity dose of Ga-OPS202 to be injected.

The actual peptide mass dose administered to the subject (injected dose) will be estimated using the following equation:

Injected dose (µg) = [Volume injected (mL) / Volume used for Ga-OPS202 preparation (mL)] x Peptide dosage in the vial (µg) = [Injected Volume/6mL] x 50µg

The radioactivity in the syringe is measured immediately before the administration of Ga-OPS202 to the subject and immediately after; the difference between these two measurements (in MBq) constitutes the radioactivity dose injected to the subject.

Ga-OPS202 will be administered twice during the study for each subject by i.v. injection over one minute prior to PET/CT scan. The PET/CT scanner settings should be the same for the two scans per subject and for all subjects at the same study site, as described in the Imaging Review Charter (IRC).

**Duration of treatment:** Ga-OPS202 will be administered i.v. twice: at Baseline/Day 1 (Visit 2), and at Visit 3, which will be 15 to 21 days after the first injection.

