## 1.2 Rationale to Conduct the Trial

The potential higher diagnostic accuracy of  $^{68}\text{Ga}$ -OPS202 (satoretide trizoxetan) PET/CT compared to pre-baseline somatostatin receptor scan warrants the progression of the compound into a phase II study to confirm the optimal dose, particularly as the analysis of the safety data of Study OPS-B-001 did not raise any concern.

The present dose-confirmation phase II study aims to define the optimal dose range for peptide mass and radioactivity based on detected number of lesions and tumour-to-background ratio in subjects with sstr2-positive GEP-NET. The study will also expand the evaluation of  $^{68}\text{Ga}$ -OPS202 safety.

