## 1.4 Peptide Mass Dose Rationale

In order to study the influence of specific activity (defined as radioactivity over peptide mass) on PET/CT image quality in the phase I/II clinical trial, two different peptide doses of  $15 \pm 5 \mu\text{g}$  and  $50 \pm 15 \mu\text{g}$  OPS202 (with  $^{68}\text{Ga}$  activity of 125 to 195 MBq) were administered to the same patient at the first and the second visit, respectively, allowing intra-patient comparison and resulting in a range of specific activity of 3 to 13 MBq/ $\mu\text{g}$ . In the proposed phase II study, the peptide ranges are designed to cover the lowest achievable peptide dose ( $5 \mu\text{g}$  to  $20 \mu\text{g}$ ; close to the  $15 \pm 5 \mu\text{g}$  of the phase I/II) and the upper range, within the capability of the kit ( $30 \mu\text{g}$  to  $45 \mu\text{g}$ ; close to the  $50 \pm 15 \mu\text{g}$  of the phase I/II).

The internationally recognized procedure guidelines for PET/CT tumour imaging with  $^{68}\text{Ga}$ -DOTA-conjugated peptides:  $^{68}\text{Ga}$ -DOTATOC,  $^{68}\text{Ga}$ -DOTANOC and  $^{68}\text{Ga}$ -DOTATATE, published by the European Association of Nuclear Medicine (EANM), which are based on the clinical experience with the known  $^{68}\text{Ga}$ -labeled somatostatin receptor agonists, proposes use of less than  $50 \mu\text{g}$  of (injected) peptide as this amount would be expected not to have clinically-significant pharmacological effect [12]. The present OPS202 kit-formulation is  $50 \mu\text{g}$

to ensure reliable radiolabeling with a  $^{68}\text{Ga}$  radionuclide incorporation greater than 97%; the upper recommended limit of 50  $\mu\text{g}$  was selected to compensate for the presence of potential metal contaminants (potential breakthrough of the parent radionuclide is possible [13] from the  $^{68}\text{Ge}/^{68}\text{Ga}$  generator elution and to provide a margin for robust radiolabeling. In the formulation given to patients, approximately 0.01-0.04% of OPS202 is complexed to  $^{68}\text{Ga}$ , whereas the remaining is unlabelled.

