For each PET assessment, lesion SUV_{max} will be measured for each of the most avid lesions identified per organ (up to a maximum of five most avid lesions per organ that are confirmed by SOT) and reported in the ICL database.

For each organ, the SUV_{max} ratio will be computed as follows:

$$SUV_{max} \text{ ratio} = \frac{SUV_{max}}{SUV_{mean} \text{ of the subject's reference tissue (tumour – free liver)}}.$$

It will be analysed using descriptive statistics, presented for:

- each of the six combinations of injected peptide/radioactivity dose range
- each of the two peptide mass dose ranges
- each of the three radioactivity dose ranges

Individual values of SUV_{max} ratio will be listed by subject, by organ and by visit.

Background location will be specified (L: Liver, B = Aortic blood).

h) SNR in the liver

SNR will be calculated from lesion-free VOI (reference tissue) using following formula:

$$SNR = \frac{SUV_{mean}}{SUV_{SD}}$$

Those SUV_{mean} and SUV_{SD} will be available in the database provided by ICL.

A higher SNR in the liver indicates higher effectiveness of ^{68}Ga -OPS202 as a diagnostic agent.

It will be analysed using descriptive statistics, presented for:

- each of the six combinations of injected peptide/radioactivity dose range
- each of the two peptide mass dose ranges
- each of the three radioactivity dose ranges

Individual values of SNR in the liver will be listed by subject and by visit.

Background location will be specified (L: Liver, B = Aortic blood).

Additional listing:

A listing of SUV measurements by lesion and per organ will be provided, including following data listed by subject and by visit:

- Lesion SUV_{mean}
- Lesion SUV_{max}
- Lesion SUV_{max} ratio
- Lesion Tumour-to-background ratio

3.2.2 *Safety*

All safety data will be included in the data listings and summary tables will be based on the Safety population and presented by combination of injected peptide/radioactivity dose range and overall.

AEs will be allocated to each combination of injected peptide/radioactivity dose range following the following rule: AEs will be allocated to the last dose of ^{68}Ga -OPS202 received, based on AE start date/time.

Same rule will be applied for analysing concomitant medications, based on treatment start date/time.

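### The tumour-to-background ratio cancels injected activity, so it should not count as evidence for choosing the radioactivity range

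*SAP*

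**What the plan says.** SAP 3.2.1.2 a) sets the level of measurement: "For each PET assessment, image quality will be quantitatively measured by the tumour-to-background ratio". For up to five of the most avid confirmed lesions per organ, "the tumour-to-background ratio will be computed as lesion SUV_{mean} divided by the SUV_{mean} of the" subject's "reference tissue (tumour-free liver or aortic blood"). The lesion values are averaged per organ. A high value is read as high effectiveness. Results are summarised by the six combinations, the two peptide ranges and the three radioactivity ranges, and under item d) also by MBq/kg.

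On use, the opening of SAP 3.2.1.2 begins "Selection of the optimal dose range for peptide mass and radioactivity of" the agent and bases that selection on the descriptive results of all secondary and exploratory endpoints, in addition to the primary. Protocol 1.2 says that the study "aims to define the optimal dose range for peptide mass and radioactivity based on detected number of lesions and tumour-to-background ratio".

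The same part of the SAP plans two other measures of image quality. One is a blinded paired quality score, the qualitative half of the same key secondary endpoint. The other is liver SNR (SUVmean/SUVSD), item h), which is exploratory.

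**The concern.** A measure that helps choose among 40-80, 100-140 and 160-200 MBq should move when MBq moves. This one divides two SUVs that share one injected activity and one body weight. Whatever activity does to image noise, the formula has no noise term.

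Two misreadings follow. A flat result could be taken to show that image quality does not depend on activity, although the protocol synopsis expects a poor diagnostic signal at 40-80 MBq. Or a difference between ranges could be read as an activity effect when it comes from subject mix, from which lesions were among the five most avid, or from liver being the reference in some subjects and aortic blood in others. SAP 3.1.5 plans no significance testing, and the listed statistics include no interval, so nothing in the output would flag such a difference as chance.

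**Working it through.** **1. Design counts.** 24 subjects × 2 scans = 48; 48/6 = 8 per combination; 48/3 = 16 per radioactivity range. These match the plan. There is no power calculation to reproduce.

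**2. Cancellation.** The documents do not define SUV. Assume the usual form: SUV = tissue concentration / (injected activity A / weight W). With lesion concentration c_T and reference concentration c_B,

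ratio = [c_T/(A/W)] / [c_B/(A/W)] = c_T/c_B.

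If both concentrations are proportional to A, the ratio is free of A and W. With assumed SUVmeans of 12 and 4 it is 3.00 at every activity from 40 to 200 MBq.

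**3. Could MBq change uptake itself?** Protocol 1.4 states that "approximately 0.01-0.04% of OPS202 is complexed to" the radionuclide. Receptor occupancy is then set by µg of peptide, and Protocol 6.1.1 derives that mass from injected volume. The synopsis adds: "The PET/CT scanner settings should be the same for the two scans per subject". This leaves noise as the main thing that activity changes. Peptide mass does not cancel: if it moved reference SUVmean from 4 to 3, the ratio would go from 3.0 to 4.0.

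**4. Second-order effect of noise.** This was simulated at the range midpoints (60, 120, 180 MBq) with voxel noise proportional to 1/√A, voxel CV 10% to 25% at 180 MBq, 20 independent voxels per lesion, and the five most avid of 10 lesions. All of these are assumptions.

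- The mean ratio departed from its true value by at most about 1.1% at 60 MBq and 0.4% at 180 MBq. The larger shifts were upward, at low activity, from picking the most avid lesions on noisier images.
- Within-scan relative SD did change: 3.0% at 60 against 1.8% at 180 MBq (voxel CV 10%), and 7.6% against 4.3% (voxel CV 25%).
- Simulated lesion SUVmax was higher at 60 than at 180 MBq: 20.42/18.37 = 1.11 at voxel CV 10% and 28.09/22.72 = 1.24 at 25%. So the remaining activity dependence of the SUVmax ratio in item g) also favours low activity.

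**5. Chance difference between two ranges.** Any two ranges share one arm. For 40-80 against 160-200 MBq that is Arm C, whose subject effects cancel. Arms A and B contribute eight different subjects each. With between-subject CV s_b and within-subject CV s_w,

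SE = √(16·s_b²/16² + 32·s_w²/16²) = √(s_b²/16 + s_w²/8).

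- s_b = 30%, s_w = 15% (assumed): √(0.005625 + 0.0028125) = 9.2% of the mean.
- s_b = 60%, s_w = 15% (assumed): √(0.0225 + 0.0028125) = 15.9%.

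The median absolute chance difference is 0.6745 × SE, or 6.2% to 10.7%, against a simulated noise effect near 1%.

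**6. What does respond to activity.** Under the 1/√A law, liver SNR relative to 180 MBq is √(60/180) = 0.58 at 60 MBq and √(120/180) = 0.82 at 120 MBq. With liver as reference,

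(lesion SUVmean − liver SUVmean)/liver SUVSD = (ratio − 1) × SNR.

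For example, at assumed voxel CV 15% at 180 MBq, (3 − 1) × 6.67 = 13.3 at 180 MBq and (3 − 1) × 3.85 = 7.7 at 60 MBq. All of the activity dependence comes from SNR.

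**The case against.** A reader might infer that this ratio is what selects the radioactivity range, and that the plan therefore cannot tell the three ranges apart. The documents do not support that. SAP 3.2.1.1 bases selection on the highest relative lesion count, and SAP 3.2.1.2 then adds every secondary and exploratory endpoint. Protocol 1.2, which names the ratio beside lesion number, is background; the objectives in Protocol 2.2 refer to detected lesions, then SUVmax and other image-quality parameters.

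A reader might also infer that the whole key secondary endpoint will be flat. Only its quantitative half is nearly so. In the other half each blinded reader compares a subject's two scans directly, and that score can respond to noise. Liver SNR is already planned by radioactivity range, and its exploratory label does not keep it out of selection.

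Nor is the insensitivity absolute. Noise affects the precision of the ratio and which lesions enter it. The rules for drawing lesion volumes are left to the imaging charter, which was not available here; a noise-dependent threshold could add some dependence. Finally, different subjects in each cell affect every endpoint, not just this one.

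All of this stands and limits the point. It does not make the ratio evidence about MBq. The quality score is there to back the ratio up, and each pair it compares also differs in peptide range and visit. SNR contains no lesion signal.

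**Conclusion.** The point holds in limited form. The mean tumour-to-background ratio is by construction nearly insensitive to radioactivity at a given peptide mass, yet the SAP reads it as effectiveness and lets it inform the radioactivity choice. Between-range differences would mostly reflect subject mix, lesion selection or choice of reference tissue, and a flat result would not show that image quality is unaffected by activity.

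The cancellation rests on the usual SUV definition and on the protocol's labelled fraction. The shift of about 1% and the standard error of 9% to 16% rest on the assumed noise and CVs above. Simulating a contrast-to-noise ratio with noise assumed to fall with activity would make it look highly discriminating; that result comes from the assumption and is not a property of this trial. It is worth correcting before the results are read, but it does not undermine the primary endpoint.

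**What to change.** In SAP 3.2.1.2:

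- State that the tumour-to-background ratio is used for the peptide-mass comparison and not to select the radioactivity range, and treat the SUVmax ratio in item g) the same way.
- State that the radioactivity choice rests on relative lesion count, the paired blinded quality score and liver SNR, and move SNR up to support the key secondary endpoint. Item h) lists the background as liver or aortic blood, so specify liver.
- Optionally, add a descriptive contrast-to-noise ratio = (lesion SUVmean − tumour-free liver SUVmean)/liver SUVSD. Use liver for both terms, compute it only where a lesion-free liver volume exists, and read it within subject on the same scanner.

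The cost is SAP wording and, if the option is taken, one derived variable and one table. Lesion SUVmean is already to be listed, and for SNR the reference SUVmean and SUVSD "will be available in the database provided by ICL". No new imaging or reading is needed. The downsides are that contrast-to-noise depends on the scanner, and that each within-subject pair also differs in peptide range and visit, because the lower peptide range is always given at Visit 2. That tie to visit also limits the peptide comparison.
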